#### 6.4.1.1 Sensitivity and Subgroup Analysis

The Phase 3b and Pooled primary, 1st secondary (severe) and the 3rd secondary (deaths) endpoints' analyses will be repeated for the following analysis:

- PP Analysis Set
- All COVID-19 cases from CRF using mITT

As indicated in Table 6, Primary and secondary endpoints assessments of different phases (3b or 1/2/3a or Pooled) will be repeated for below subgroups. A forest plot of VE% will be provided for each subgroup analysis

- Risk group
- Sex
- Region
- Study site

#### 6.4.2 Secondary Analysis

The analysis of secondary endpoints will follow the same methods of primary analysis. Subgroup analysis will be performed for each endpoint and phase (3b, 1/2/3a and 1/2/3b) as indicated in Table 6. Kaplan-Meier plots will be provided for each endpoint.

##### 6.4.2.1 Severe COVID-19

The first occurrence of confirmed, protocol-defined severe COVID-19 with onset between Day 36 and Day 92 inclusive. This endpoint includes confirmed, protocol-defined severe COVID-19

and death due to confirmed, protocol-defined COVID-19, as confirmed by the blinded Independent Adjudication Committee and adjudicated for severity.

Time at risk = [Last date at risk – (Date received 2nd dose + 7 days)]+1; where the last date at risk will be defined as COVID-19-event date or censor date, whichever comes first.

The analysis will follow the same methods as for the first primary endpoint.

#### **6.4.2.2 COVID-19 Any Time After Vaccination (Without Prior COVID-19)**

The first occurrence of confirmed, protocol-defined COVID-19 with onset at any time after the first dose of study vaccine administration and up to Day 92 inclusive; ITT who have received any dose of study vaccine in the first vaccination series, with no evidence of infection (i.e. positive RT-PCR test or seropositivity for anti-nucleocapsid antibody) prior to vaccination on Day 1.

Time at risk = [Last date at risk – Date received 1st dose]+1; where the last date at risk will be defined as COVID-19-event date or censor date, whichever comes first.

#### **6.4.2.3 Death Due to COVID-19**

The occurrence of death attributed to COVID-19 occurring between Day 36 and Day 92 inclusive.

Time at risk = [Last date at risk – (Date received 2nd dose + 7 days)]+1; where the last date at risk will be defined as date of death attributed to COVID-19 or censor date, whichever comes first. The corresponding onset date of COVID-19 will be between Day 36 and Day 92 inclusive.

#### **6.4.2.4 COVID-19 After Both Vaccines and Regardless of Baseline SARS-CoV-2 Serostatus**

The efficacy of ARCT-154 and placebo for the prevention of virologically confirmed COVID-19 regardless of baseline serostatus for evidence of prior SARS-CoV-2 infection with onset between Day 36 and Day 92 inclusive, based on participants who received both protocol-required doses of study vaccine with no SARS-CoV-2 infection between Day 1 and Day 35, but including those who are seropositive at baseline (Day 1).

Time at risk = [Last date at risk – (Date received 2nd dose + 7 days)]+1; where the last date at risk will be defined as COVID-19-event date or censor date, whichever comes first.

### **6.4.3 Exploratory Analysis**

The analysis of exploratory endpoints will follow the same methods of primary analysis and will be performed for Phase 3b and Pooled. Kaplan-Meier plots will be provided for each endpoint.

#### **6.4.3.1 Severe COVID-19 After First Vaccination**

The first occurrence of confirmed, protocol-defined severe COVID-19 with onset at any time after the first dose of study vaccine administration and up to Day 92; ITT that have received any dose of study vaccine in the first vaccination series, with no evidence of infection (i.e. positive RT-PCR test or seropositivity for anti-nucleocapsid antibody) prior to vaccination.

Time at risk = [Last date at risk – Date received 1st dose]+1; where the last date at risk will be defined as COVID-19-event date or censor date, whichever comes first.

#### **6.4.3.2 COVID-19 Death After First Vaccination**

The occurrence of death attributed to COVID-19 occurring at any time after the first dose of study vaccine administration and up to Day 92; ITT that have received any dose of study vaccine in the first vaccination series, with no evidence of SARS-CoV-2 infection (i.e. positive RT-PCR test or seropositivity for anti-nucleocapsid antibody) prior to vaccination.

Time at risk = [Last date at risk – Date received 1st dose]+1; where the last date at risk will be defined as death date or censor date, whichever comes first.

#### **6.4.3.3 COVID-19 After First Vaccination**

The first occurrence of confirmed, protocol-defined COVID-19 with onset at any time after the first dose of study vaccine administration and up to Day 92; ITT that have received any dose of study vaccine in the first vaccination series.

Time at risk = [Last date at risk – Date received 1st dose]+1; where the last date at risk will be defined as COVID-19-event date or censor date, whichever comes first.

#### **6.4.3.4 COVID-19 by SARS CoV-2 variants**

The first occurrence of confirmed, protocol-defined COVID-19 with onset between Day 36 and Day 92 inclusive will be presented by SARS COV-2 variants as frequency table for mITT. The first occurrence of confirmed, protocol-defined COVID-19 for all participants infected with the same variant (Delta, Omicron, Not undetermined) of SARS-CoV-2, with onset between Day 36 and Day 92 inclusive, will be analyzed for mITT.

Similar analysis will be performed for the first occurrence of confirmed, protocol-defined COVID-19, with onset at any time after the first study vaccination and up to Day 92, based on ITT that have received any dose of study vaccine in the first vaccination series, with no evidence of infection prior to vaccination (defined as no positive RT-PCR or other COVID-19 test or seropositivity for anti-nucleocapsid antibody prior to Day 1 vaccination).

#### 6.4.3.5 Severe COVID-19 by SARS CoV-2 variants

The first occurrence of confirmed, protocol-defined severe COVID-19 with onset between Day 36 and Day 92 inclusive will be presented by SARS COV-2 variants as frequency table for mITT. The first occurrence of confirmed, protocol-defined severe COVID-19 for all participants infected with the same variant (Delta, Omicron, Not determined) of SARS-CoV-2, with onset between Day 36 and Day 92 inclusive, will be analyzed for mITT.

Similar analysis will be performed for the first occurrence of confirmed, protocol-defined severe COVID-19, with onset at any time after the first study vaccination and up to Day 92, based on ITT that have received any dose of study vaccine in the first vaccination series, with no evidence of infection prior to vaccination (defined as no positive RT-PCR or other COVID-19 test or seropositivity for anti-nucleocapsid antibody prior to Day 1 vaccination).

### 6.5 Immunogenicity Evaluations

The immunogenicity assays were measured at 2 different laboratories:

1. Assays performed at National Institute of Hygiene and Epidemiology (NIHE), Department of Virology, Vietnam. These are regarded as protocol defined primary endpoints for analysis of immune responses in Phase 1/2/3a.
  - a. Serum NAb titer against SARS-CoV-2:
    - i. Genscript SARS-CoV-2 sVNT
    - ii. PRNT50
      1. Ancestral-clinical isolate
      2. Delta-clinical isolate
  - b. Serum IgG antibodies binding the SARS-CoV-2 spike protein (BAb)-Siemens Advia platform
2. Validated Assays performed at PPD BioA Labs in Richmond, VA, USA. These are regarded as supportive endpoints for the analysis of immune responses in Phase 1/2/3a.
  - a. Serum NAb titer against SARS-CoV-2: Pseudovirus microneutralization test (MNT)
    - i. D614G VAC62 (validated)
    - ii. Delta VAC120 (validated)
    - iii. Omicron BA.1 VAC122 (validated)
  - b. BAb by Mesoscale Discovery (MSD) multiplex: Ancestral V72 (validated)

- c. Angiotensin-converting enzyme 2 (ACE2)/sVNT (exploratory): Multiplex variants VAC114

Even though the sVNT assay performed at National Institute of Hygiene and Epidemiology (NIHE) was defined on the protocol as primary, following regulatory interactions it was agreed to use a validated assay (i.e. MNT performed at PPD) for this investigation. Appendix 9.3 provides an overview of the assay measured in the study along with analysis sample timepoints available for each phase.

Immunogenicity data from participants in Phases 1, 2 and 3a will be pooled for analysis up to Day 92 and will include participants who received the first two doses of study vaccine (referred as 2 dose schedule). Participants in Phase 2 and 3a that received ARCT-154 in the initial vaccination series are further randomized to receive a 3rd vaccination of either ARCT-154 or placebo at Day 92 followed by placebo at Day 120. Therefore, after Day 92 only data from Phase 2/3a will be pooled (referred as 3 dose schedule). Additional analyses will be performed to report Phase 1 data up to day 120 separately. Phase 3c immunogenicity samples were not tested and therefore no immunogenicity analysis will be performed on the phase 3c participants (refer to section 7.1 for rationale).

Immunogenicity analyses will be performed on Immunogenicity analysis sets as defined in section 4.1. Sensitivity analyses will be performed on the immunogenicity PP sets as defined in section 4.1; selection of participants included in the analyses on the PP sets at various analysis timepoints will be performed as described in section 5.5.

The primary immunogenicity estimand for the Phase 1/2/3a substudy along with handling of intercurrent events is described in section 9.2.1. For analyses performed on Phase 1/2/3a sets (two dose schedule), participant's immunogenicity data after switchero/receipt of further study vaccine, non-study COVID-19 vaccine (Intercurrent event 2) or confounding on-study medications (intervent event 5) will be excluded from the analysis. For analysis performed on Phase 1 and Phase 2/3a (three dose schedule) sets, participant's immunogenicity data after non-study COVID-19 vaccine or confounding on-study medications will be excluded from the analysis.

Section 6.5.1 provides an overview of the immunogenicity analyses while sections 6.5.2 to 6.5.6 provides a description of analyses (including analysis sets and timepoints) that will be performed for each parameter. Section 6.5.7 described immunogenicity analyses performed by subgroup.

The following analyses and definitions will be used. No p-values will be calculated:

- Number and proportion (along with Exact Clopper-Pearson 95% CI) of participants achieving antibody seroconversion as defined below (FDA defined), by timepoint and treatment arm:
  - For participants with Day 1 (baseline) antibody concentration < LLOQ, seroconversion is defined as  $\geq$  4-fold increase from LLOQ.
  - For participants with Day 1 antibody concentration  $\geq$  LLOQ, seroconversion defined as  $\geq$  4-fold increase from Day 1 antibody concentration

An additional definition (protocol defined) of seroconversion will be applied as follows:

- For participants with Day 1 (baseline) antibody concentration < LLOQ, seroconversion defined as  $\geq$  4-fold increase from LLOQ/2.
- For participants with Day 1 (baseline) antibody concentration  $\geq$  LLOQ, seroconversion defined as  $\geq$  4-fold increase from Day 1 antibody concentration

Seroconversion at D120 will be assessed using both Day 1 and Day 92 as reference.

- Geometric Mean Concentration (or Titer) (GMC or GMT) and corresponding 95% CI, minimum and maximum concentration, by timepoint and treatment arm
- GMC (or GMT) ratio of ARCT-154 versus placebo and corresponding 95% CI by timepoint (not applicable for three dose-schedule analysis)
- Geometric Mean Fold Rise (GMFR) and corresponding 95% CI at each timepoint, from Day 1 (and additionally from Day 92 for Day 120 where applicable) by treatment arm.

Reverse cumulative functions will be presented for each assay by treatment arm and post baseline timepoint. Antibody levels will be presented on x axis in log10 scale.

Geometric mean concentration (GMC) is the geometric mean of the antibody concentration and is derived as follows:

$$GMC = \ln^{-1} \left( \frac{\sum_{i=1}^n \ln X_i}{n} \right), \text{ where } X: \text{antibody concentration}$$

The GMC ratio at timepoint D is the ratio of ARTC-154 GMC obtained at timepoint D over placebo GMC obtained at timepoint D.

$$\text{GMC ratio at Day D} = \frac{\text{ARTC-154 GMC at Day D}}{\text{Placebo GMC Day D}}$$

GMFR is defined as the geometric mean of fold rise of post-study intervention concentrations over the Day 1 (baseline) concentration. These will be calculated as follows:

$$GMFR = \ln^{-1} \left( \frac{\sum_{i=1}^n \ln \left( \frac{X_2}{X_1} \right)}{n} \right),$$

where X2 is the antibody concentration at time point of evaluation and X1 is the antibody concentration at baseline (or Day 92).

Handling of immune response concentration below LLOQ or greater than ULOQ is described in section 5.2.

Conversion factors to be applied to immunogenicity parameters are summarized in section 9.4.

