
	
adequately tolerated by SRC and the MOH, the study will initiate simultaneous enrollment of both Phase 2 and Phase 3a.
 
In Phase 2, which expands the safety and immunogenicity characterization of the study vaccine in a larger group of participants, 300 participants will be randomly assigned 3:1 to receive ARCT-154 or placebo (225:75) for the initial series of vaccinations.
 
In Phase 3a, which expands the enrollment further to include 600 participants who will be randomly assigned 3:1 to receive ARCT-154 or placebo (450:150) for the initial series of vaccinations. After completion of enrollment of Phases 2 and 3a, the SRC and MOH will independently review available blinded safety data through at least 7 days (Day 8) post-first vaccination and, if study vaccination is judged to be adequately tolerated by SRC and the MOH, the study will initiate enrollment of Phase 3b. The second dose of study vaccine will not be administered to participants in Phase 3b until the SRC has reviewed the Phases 2 and 3a safety data through 7 days post-second vaccination (Day 36) and judged that study vaccine is adequately tolerated. Data from participants in Phase 1, Phase 2, and Phase 3a will be pooled for a primary analysis of immunogenicity at Day 57. Data from this analysis will be submitted to the Vietnamese Ministry of Health for evaluation for potential emergency use authorization (EUA). Data from Phase 2 and 3a will also be pooled to allow comparison of immunogenicity following the 3rd dose (immune responses at Day 120 with that after the 2nd dose (immune responses at Day 57).
 
In Phase 3b, approximately 16,000 participants will be randomly assigned 1:1 to receive ARCT-154 or placebo for the initial series of vaccinations. Phase 3b constitutes the Exploratory Efficacy Subgroup. Data from this subgroup will support regulatory filings along with immunogenicity data from Phase 1/2/3a and 3c. Participants in this Phase 3b portion of the study will contribute substantially to the safety analyses of ARCT-154.
 
Phase 3c will enroll approximately 2,400 participants randomized 1:1 to receive ARCT-154 or ChAdOx1. A subset of these enrolled participants (the first 1,500 enrolled in Phase 3c) will form an Immunogenicity Noninferiority Subgroup (Phase 3c-1). Day 57 data from 800 participants in this Subgroup will be used to establish the noninferiority of immunogenicity of ARCT-154 vaccine as compared to ChAdOx1, a licensed comparator vaccine. These data, along with an analysis of safety from participants exposed to ARCT-154 and followed for a median period of 2 months (60 days) may be submitted to health authorities for evaluation for a Marketing Authorization or EUA dependent on jurisdiction.
 
Phase 1 participants must be <60 years of age. Phase 2, 3a, 3b and Phase 3c participants will include elderly (≥ 60 years) participants as well. Phase 3b will enrich for participants at higher risk for COVID-19 by attempting to enroll individuals considered at high risk due to their workplace environment or living conditions.
 
For Phase 2, 3a, 3b and Phase 3c, prior to randomization, participants will be stratified by age (< 60 or ≥ 60 years of age) and for participants < 60 years of age by risk of severe COVID-19. Participants will be defined as “at risk” if they are 60 years of age or older OR have medical history described as putting the individual at risk or possibly at risk of severe coronavirus disease 2019 (COVID-19) (Appendix 5). As the eligibility criteria for Phase 1

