3.1 Phase 1/2/3a Substudy

Immunogenicity data from participants in Phases 1, 2 and 3a will be pooled for analysis up to Day 92. With implementation of protocol version 8.0, participants in Phase 2 and 3a that received ARCT-154 in the initial vaccination series are further randomized to receive a 3rd vaccination of either ARCT-154 or placebo at Day 92 followed by placebo at Day 120 in order to compare immunogenicity after 3 injections of ARCT-154 with that after 2 injections.

Therefore, after Day 92 only data from Phase 2/3a will be pooled and will be displayed separately from participants in Phase 1.

Safety data from participants in Phase 2/3a will be pooled for all time points and will be displayed separately to safety data from Phase 1.

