5. To assess the neutralizing antibody (NAb) responses by surrogate virus neutralization test to ARCT-154 following 2 (Day 57) and 3 (Day 120) vaccinations with ARCT-154 in Phase 2/3a participants	
Neutralizing antibody (NAb) responses by surrogate virus neutralization test (svNT) will be evaluated at Day 1 (baseline), Day 57 and Day 120 for assessment of seroconversion in all participants in the Phase 2/3a IAS that received ARCT-154 in the initial vaccination series
 
• The endpoint is defined as the proportion of participants that demonstrate seroconversion (defined as: 4-fold increase in antibody concentration from baseline). 
Data will be summarized according to use of international reference standards, if available.

6. To assess the IgG binding antibody responses to ARCT-154 following 2 (Day 57) and 3 (Day 120) vaccinations with ARCT-154 in Phase 2/3a participants	
IgG antibody binding the full-length SARS-CoV-2 spike protein (binding antibody [BAb]) responses will be evaluated at Day 1 (baseline), Day 57 and Day 120 in all participants in the Phase 2/3a IAS that received ARCT-154 in the initial vaccination series.
 
The following endpoints will be assessed:
 
○ Geometric mean antibody concentration (GMC)○ Increase in antibody levels from baseline (GMFR)○ Proportion of participants in each study vaccine group with seroconversion. 
Data will be summarized according to use of international reference standards, if available.

Abbreviations: COVID-19=coronavirus disease 2019

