In Phase 3a, which expands the enrollment further to include 600 participants, who will be randomly assigned 3:1 to receive ARCT-154 or placebo (450:150) for the initial series of vaccinations. After completion of enrollment of Phases 2 and 3a, the SRC and MOH will independently review available blinded safety data through at least 7 days (Day 8) post-first vaccination and, if study vaccination is judged to be adequately tolerated by SRC and the MOH, the study will initiate enrollment of Phase 3b. The second dose of study vaccine will not be administered to participants in Phase 3b until the SRC has reviewed the Phase 2 and Phase 3a safety data through 7 days post-second vaccination (Day 36) and judged that study vaccine is adequately tolerated. Data from participants in Phase 1, Phase 2, and Phase 3a will be pooled for a primary analysis of immunogenicity at Day 57. Data from this analysis will be submitted to the Vietnamese Ministry of Health for evaluation for potential emergency use authorization (EUA). Data from Phase 2 and 3a will also be pooled to allow comparison of immunogenicity following the 3rd dose (immune responses at Day 120 with that after the 2nd dose (immune responses at Day 57).

In Phase 3b, approximately 16,000 participants will be randomly assigned 1:1 to receive ARCT-154 or placebo for the initial series of vaccinations. Phase 3b constitutes the Exploratory

Efficacy Subgroup. Data from this subgroup will support regulatory filings along with immunogenicity data from Phase 1/2/3a and 3c. Participants in this Phase 3b portion of the study will contribute substantially to the safety analyses of ARCT-154.

Phase 3c will enroll approximately 2,400 participants randomized 1:1 to receive ARCT-154 or ChAdOx1. A subset of these enrolled participants (the first 1,500 participants enrolled in Phase 3c) will form an Immunogenicity Noninferiority Subgroup (Phase 3c-1); the remaining ~900 participants will form Phase 3c-2. Day 57 data from 800 participants in this Subgroup will be used to establish the noninferiority of immunogenicity of ARCT-154 vaccine as compared to ChAdOx1, a licensed comparator vaccine. These data, along with an analysis of safety from participants exposed to ARCT-154 and followed for a median period of 2 months (60 days) may be submitted to health authorities for evaluation for a Marketing Authorization or EUA dependent on jurisdiction.

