3. To assess the neutralizing antibody immune responses to ARCT-154 to SARS-CoV-2 variants of concern (VOC)/variants of interest (VOI) following 2 and 3 vaccinations with ARCT-154	
Blood samples from post-vaccination timepoints evaluated for immune responses to SARS-CoV-2 VOC/VOI.
 
The following assays will be used:
 
 
• ACE2/sVNT (Phase 1/2 IAS at Day 1 and Day 57)
 
• MNT (Phase 1/2/3a IAS at Day 1, Day 57 and Day 92; Phase 2/3a at Day 1, Day 57, Day 92 and Day 120)
 

4. To assess neutralizing antibody responses using a pseudovirus microneutralization test (MNT) following 2 (Day 57) and 3 (Day 120) vaccinations with ARCT-154	
NAb responses by MNT evaluated for the following groups/timepoints:
 
 
• Phase 1/2/3a IAS at Day 1, Day 57, Day 92
 
• Phase 2/3a IAS at Day 1, Day 57, Day 92 and Day 120
 
 
The following endpoints will be assessed:
 
 
• GMC
 
• Increase in antibody levels from baseline (GMFR)
 
• Proportion of participants in each study vaccine group with seroconversion
 

5. To assess neutralizing antibody responses by surrogate virus neutralization test to ARCT-154 following 2	NAb responses by sVNT evaluated at Day 1 (baseline), Day 57, and Day 120 for assessment of seroconversion in Phase 2/3a IAS that received ARCT-154 in the initial vaccination series

(Day 57) and 3 (Day 120) vaccinations with ARCT-154 in Phase 2/3a participants	
 
The endpoint is defined as the proportion of participants that demonstrate seroconversion (defined as: 4-fold increase in antibody concentration from baseline).
 
 
Data will be summarized according to use of international reference standards, if available.

6. To assess the IgG binding antibody responses to ARCT-154 following 2 (Day 57) and 3 (Day 120) vaccinations with ARCT-154 in Phase 2/3a participants	
IgG antibody binding the full-length SARS-CoV-2 spike protein (binding antibody [BAb]) responses evaluated at Day 1 (baseline), Day 57 and Day 120 in all participants in the Phase 2/3a IAS that received three doses of study vaccine. The following endpoints will be assessed:
 
 
GMC
 
Increase in antibody levels from baseline (GMFR)
 
Proportion of participants in each study vaccine group with seroconversion
 

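### SAP 6.5 gives no Day 120/Day 57 fold rise or interval, although the protocol pools Phase 2/3a to compare the response after dose 3 with that after dose 2

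*SAP*

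**What the plan says.** The protocol names the comparison. The synopsis states: "Data from Phase 2 and 3a will also be pooled to allow comparison of immunogenicity following the 3rd dose (immune responses at Day 120". Section 4.4 repeats the sentence and completes it "with that after the 2nd dose (immune responses at Day 57". Section 3.1 says that initial ARCT-154 recipients in Phases 2 and 3a are re-randomised "in order to compare immunogenicity after 3 injections of ARCT-154 with that after 2 injections". The same people are sampled on both days: under exploratory objective 6 (3.1.3), binding antibody is "evaluated at Day 1 (baseline), Day 57 and Day 120 in all participants in the Phase 2/3a IAS that received ARCT-154" in the initial series. SAP Table 1 keeps the framing, with objectives "following 2 (Day 57) and 3 (Day 120) vaccinations with ARCT-154".

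The endpoints are more general than that sentence. Objectives 4 and 6 list the GMC, the GMFR from baseline and seroconversion. Objective 5 lists seroconversion only. Protocol 8.7.3.1 defines the GMFR against a reference time point that it leaves open, with baseline as an example.

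SAP 6.5 settles the reference. GMFR is given "from Day 1 (and additionally from Day 92 for Day 120 where applicable) by treatment arm", and the formula allows only baseline or Day 92 as denominator. For seroconversion: "Seroconversion at D120 will be assessed using both Day 1 and Day 92 as reference". GMCs are given with a 95% CI for each time point and arm. The one GMC ratio is ARCT-154 against placebo, and it is marked as not applying to the three-dose analyses. Table 7 lists GMC, GMFR and seroconversion rate for the three-dose schedule, and 6.5 rules out p-values. Section 7 does not mention a Day 120/Day 57 contrast.

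**The concern.** The protocol gives one purpose for carrying the pooled Phase 2/3a data past dose 3, which is to set Day 120 against Day 57. The design supplies both measurements on each participant, so the natural estimate is a within-person ratio with a paired interval. The planned output does not contain it.

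A reader who wants the comparison has two routes. One is to set two separately estimated GMCs, or two Day 1 fold rises, side by side. Neither route gives an interval for their ratio. The other is to take the Day 120/Day 92 fold rise as the gain of dose 3 over dose 2. That ratio is paired, but its reference is the level just before dose 3 and not the response after dose 2. If antibody falls between Day 57 and Day 92, it will look more favourable than the comparison the protocol describes.

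**Working it through.** The documents give no sample size, power or precision for this contrast, so there is no figure to reproduce. The check covers what the planned output can yield and what a paired interval would add.

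**Inputs**
- Initial ARCT-154 recipients: 225 in Phase 2 and 450 in Phase 3a (Protocol 4.1), total 675.
- Re-randomisation 3:1 at Day 92 (Protocol 4.5.2): 675 × 3/4 ≈ 506 to a third ARCT-154 dose and 675 × 1/4 ≈ 169 to placebo, before attrition.
- Samples: SAP 9.3 lists Day 57 and Day 120 results in Phases 2 and 3a for sVNT, binding antibody (Siemens) and MNT.
- Log-scale SD: not given for this contrast. The only variability figure is the Phase 3c MNT coefficient of variation of 4.6 (Protocol 8.5.3). Read as a ratio under a log-normal model, it gives √ln(1 + 4.6²) = 1.76. Range used: 0.8 to 1.76, equal on both days.
- Within-person correlation ρ between Day 57 and Day 120: not given. Range used: 0.3 to 0.7.

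**Step 1: point estimate.** On complete pairs, mean(ln X₁₂₀) − mean(ln X₅₇) = mean(ln X₁₂₀ − ln X₅₇). The ratio of the two GMCs, the ratio of the two Day 1 GMFRs and the paired GMFR are therefore the same number. A simulated data set (n = 506, SD 1.2, ρ = 0.6) gave 1.633 for all three.

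**Step 2: interval.** Treating the days as independent, SE = s√(2/n). Paired, SE = s√(2(1−ρ)/n). The ratio of log-scale widths is √(1−ρ):

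| ρ | √(1−ρ) | Paired CI narrower by |
|---|---|---|
| 0.3 | 0.84 | 16% |
| 0.5 | 0.71 | 29% |
| 0.7 | 0.55 | 45% |

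For n = 506, the 95% CI is the estimate multiplied and divided by exp(1.96 × SE):

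| SD(ln) | Independent | Paired, ρ = 0.3 | ρ = 0.5 | ρ = 0.7 |
|---|---|---|---|---|
| 0.8 | 1.104 | 1.086 | 1.072 | 1.055 |
| 1.2 | 1.159 | 1.132 | 1.110 | 1.084 |
| 1.76 | 1.242 | 1.199 | 1.166 | 1.126 |

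**Step 3: can the paired interval be recovered from the planned tables?** No. The GMC intervals give the variance at each day. The Day 1 fold-rise intervals add each day's covariance with Day 1, and the Day 92 fold rise adds the covariance of Day 92 with Day 120. None contains the covariance of Day 57 with Day 120, which is what the paired SE needs.

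**Step 4: the Day 92 reference.** X₁₂₀/X₉₂ = (X₁₂₀/X₅₇) × (X₅₇/X₉₂). The last factor is 1 with no decline, 1/0.75 = 1.33 with a 25% fall and 1/0.5 = 2 with a 50% fall. The falls are illustrative, since the documents give no waning figure.

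**Step 5: incomplete pairs.** SAP 6.5 drops results after a non-study vaccine or confounding medication. The Day 57 and Day 120 GMCs may then rest on different people, and the equality in Step 1 no longer holds exactly.

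**The case against.** The strongest reply is that the plan delivers its objectives as worded. Objectives 4 to 6 set out to assess responses on the two days and define no Day 120/Day 57 ratio. The comparison sentence explains the pooling and names no statistic or interval. Table 7 reports the listed endpoints on both days. Everything here is exploratory and descriptive, with no decision rule, and on complete pairs the point estimate is not harmed. All of this stands, and it sets the weight of the point. It does not supply the missing interval for a comparison that the protocol states twice.

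The Day 92 fold rise is a legitimate measure of the boost over the pre-dose level and should stay. Day 57 results are reported too, so waning would be visible.

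Timing also counts. SAP 2.5 says that the 6-month analysis had already presented immunogenicity to Day 120. SAP 2.4 says that some authors of this SAP had access to participant-level unblinded data from earlier analyses. A new main estimate named now would be post hoc, so the addition should be supplementary and labelled as such.

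Three stronger readings are tempting, and the documents support none of them:
- **That the SAP changed the reference day without logging it.** The protocol endpoints already use the rise from baseline. The SAP keeps Day 1 and adds Day 92, and Day 57 was never the specified denominator.
- **That the SAP analyses the two days as independent samples.** It prescribes no method for comparing them. That step would be the reader's.
- **That a planned test loses substantial power.** No test is planned, nor any rule based on whether the separate intervals overlap. The protocol's limit of MNT to the first 150 Phase 2 recipients is also not carried into the SAP, which takes MNT across the Phase 2/3a set.

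**Conclusion.** The point holds as a gap in the planned output. The protocol says Phase 2/3a are pooled to compare Day 120 with Day 57, the same participants supply both values, and SAP 6.5 and Table 7 produce no estimate or interval for that contrast.

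The loss on complete pairs is in precision. At 506 third-dose recipients with SD(ln) 1.76 and ρ = 0.5, the interval would be a factor of 1.166 either side of the estimate, against 1.242 if the days were treated as independent. With SD 0.8 the factors are 1.072 and 1.104. These rest on an assumed correlation, an SD range whose upper end is borrowed from the Phase 3c sample-size assumption, and planned numbers without attrition. No primary or secondary conclusion depends on it. The point concerns the within-person contrast only, not the comparison of re-randomised arms at Day 120.

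**What to change.** In SAP 6.5, for the Phase 2/3a three-dose-schedule analyses of sVNT, binding antibody and MNT, add the paired GMFR at Day 120 from Day 57 with a 95% CI. Give it by re-randomised arm, in participants with both results, and state the number of pairs. Present it as a supplementary descriptive estimate beside the Day 1 and Day 92 GMFRs, leaving the protocol endpoints unchanged. Record in SAP Section 7 that it was added after the earlier Day 120 analysis.

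The cost is a sentence in 6.5, an entry in Section 7 and one more reference day in an existing GMFR program. No new samples or assays are needed.
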